12.5 ANALYSIS POPULATIONS

The per-protocol analysis population includes all subjects who have at least one post-treatment visit and have no major protocol deviations, including specifically no use of dry-eye medications (Xiidra, Restasis). The primary and secondary endpoint analyses will be carried out on the per-protocol population. The primary analysis population will be per-protocol.

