At 1 month follow-up, TearCare subjects demonstrated an improvement from baseline in mean (\pm SD) TBUT of 11.7 ± 2.6 seconds compared with an average worsening of -0.3 ± 1.1 seconds for subjects in the warm compress group ($p<0.0001$). Significantly greater improvements in the change from baseline in meibomian gland scores, as well as corneal and conjunctival staining scores were observed in the TearCare group. Subjects in the TearCare group also showed significantly greater improvement in dry eye symptoms as measured by the three questionnaires.

No adverse events were reported in either group.

Table 1: TearCare System – Pilot Study Results (2017)

	TearCare (n=24 eyes, 12 subjects)			Warm Compress control (n=24 eyes, 12 subjects)		
	Baseline	4 weeks	6 months	Baseline	4 weeks	6 months
Tear Break-up Time (sec) – Mean (SD)	3.1 (0.8)	14.8 (2.6)	7.9 (1.5)	3.3 (1.0)	3.1 (0.8)	3.0 (1.0)
Dry Eye Symptom Questionnaires						
Total OSDI Score (0 to 100)	41.0 (18.4)	15.7 (12.2)	30.3 (15.1)	33.0 (19.9)	24.6 (15.2)	30.3 (15.1)
Total SPEED Score (0 to 28)	15.7 (5.2)	7.8 (3.5)	8.2 (6.0)	14.4 (3.8)	12.6 (3.3)	12.2 (4.0)
Total SANDE Score	64.9 (25.9)	40.2 (18.8)	45.9 (30.5)	55.9 (31.5)	57.5 (25.7)	62.1 (21.8)
Meibomian Gland Assessment						
Total Meibomian Gland Score (0 to 45)	6.3 (3.6)	41.0 (2.1)	31.5 (5.5)	9.0 (4.3)	8.2 (4.0)	9.4 (3.5)
# Glands Secreting Any Liquid (0 to 15)	0.8 (0.9)	14.6 (0.8)	11.5 (2.4)	1.3 (1.7)	1.3 (1.6)	1.7 (1.5)
# Glands Yield Clear Liquid (0 to 15)	0.0 (0.0)	11.4 (1.6)	5.4 (3.0)	0.3 (0.7)	0.0 (0.0)	0.1 (0.4)
Corneal Staining Score (0 to 15)	3.5 (1.8)	0.2 (0.4)	3.2 (2.6)	3.4 (2.9)	3.2 (2.6)	3.2 (2.8)
Conjunctival Staining Score (0 to 15)	3.7 (2.5)	0.1 (0.3)	0.3 (0.7)	3.0 (3.4)	4.1 (3.5)	3.2 (3.1)

Conclusions

The TearCare Group consistently showed a significant improvement between the baseline and 4 weeks follow-up for all outcome measures, whereas the Warm Compress group did not. For all outcome measures, the TearCare Group's mean change between baseline and 4 weeks follow-up was better than the Warm Compress group. These results were maintained out to 6 months.

This pilot study provided preliminary evidence of the safety and effectiveness of the TearCare device in relieving the signs and symptoms of dry eye.

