9.5.4 MANAGEMENT OF DRY EYE SYMPTOMS DURING FOLLOW-UP

During follow-up, if subjects require relief of their dry eye symptoms, they should only use Refresh® Plus drops. Other types of over-the-counter lubricants should not be used. Subjects should record their daily use of lubricants on the Lubricant Drop log.

Subjects **should not use** any other method of relieving dry eye symptoms, including any of the following:

- Warm compress
- Restasis or Xiidra
- Other dry eye treatments (e.g. Lipiflow, TrueTear, iLux, punctal plugs, etc.)
- Lubricants other than Refresh Plus

NOTE: If a subject had a punctal plug at the baseline visit and it falls out during the study, it should be replaced.

Review these instructions with subjects at the end of the Baseline visit and provide them with the Lubricant Drop log. They should complete the log each day and bring it back to the clinic at the 1 month follow-up visit.

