11.6 STEPS THAT WILL BE TAKEN TO CONTROL OR MITIGATE THE RISKS

The major risks to the subjects and the steps taken to control or mitigate them are described below:

1. Overheating of the eyelids: All TearCare treatments will be done in the investigator's office under direct supervision of the investigator. The device delivers heat to the eyelids at a temperature ranging from 41-45°C. This temperature range was selected because it is both safe for eyelid heating and effective for melting obstructions in the meibomian glands.^{24,25,26,27} The user can adjust the temperature up or down to a level that is comfortable, and may also shut off the System at any time if it is too uncomfortable or painful. In addition, the TearCare System continuously monitors and regulates the temperature at the tissue-contacting surface of the iLid devices and has been designed to not exceed the maximum allowable temperature.
2. Corneal abrasion: If the iLid devices are not positioned properly or come loose during the treatment, there is the potential for a corneal abrasion. To mitigate this, the supervising physician will apply the strips to the subject and will monitor their position during the treatment to ensure they remain in place and secure.

In addition, there is the possibility of corneal abrasion or abrasion of the eyelid surface during expression of the meibomian glands. To reduce the chance of abrasion, the forceps have been designed with smooth surfaces (i.e. no rough edges) and only trained users will perform expression.

²⁴ Lane SS, DuBiner H, Epstein RJ, et al. A New System, the LipiFlow, for the Treatment of Meibomian Gland Dysfunction. *Cornea*. 2012; 31 : 396-404

²⁵ Blackie CA, Solomon JD, Greiner JV, Holmes M, Korb DR. Inner Eyelid Surface Temperature as a Function of Warm Compress Methodology. *Optom Vis Sci* 2008;85:675-683.

²⁶ Moritz AR, Henriques FC. Studies of thermal injury: the relative importance of time and surface temperature in the causation of cutaneous burns. *Am J Pathol* 1947;23:695-720.

²⁷ Medical electrical equipment Part 1: General requirements for basic safety and essential performance (IEC 60601-1).

3. Worsening of dry eye symptoms: It is possible that subjects will experience a worsening of dry eye symptoms during the study. Subjects will undergo a complete eye exam at each visit and if any untoward or worsening signs of ocular surface disease are observed, they will be treated appropriately.

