12.4 EVALUABILITY

All subjects on whom the TearCare device is attempted will be considered evaluable for the safety analysis. All eyes that have at least one follow-up visit and have no major protocol deviations will be evaluable for the per protocol analysis.

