15 PROTOCOL MODIFICATIONS AND DEVIATIONS

Protocol modifications may occur during the study. Each will be approved by the sponsor before implementation. Each will undergo Institutional Review Board (IRB) review and approval, as necessary.

Any deviations from this protocol intended to protect the life or physical well-being of a subject in an emergency are to be reported to Sight Sciences, Inc. as well as the IRB as soon as possible, and no later than 5 working days after the emergency occurred.

All protocol deviations will be documented using the Protocol Deviation form.

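### Per-protocol is the only effectiveness population in 12.5, and its drug-use exclusion could remove some poor responders and modestly raise the single-arm mean change

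*Combined protocol and SAP*

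**What the plan says.** All references are to the combined protocol and SAP.

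- **Effectiveness population (12.5).** "The primary and secondary endpoint analyses will be carried out on the per-protocol population". Members need at least one post-treatment visit and must "have no major protocol deviations, including specifically no use of dry-eye medications (Xiidra, Restasis". The definition is by subject. It does not say when the drug use must occur, and 'major' is not defined further.
- **Evaluability (12.4).** The same requirement is put in terms of eyes: "All eyes that have at least one follow-up visit and have no major protocol deviations will be evaluable for the per protocol analysis". The set of all subjects in whom treatment was attempted is defined for safety only.
- **Permitted and barred relief (9.5.4).** Refresh Plus is the only lubricant allowed, and its use is logged. Subjects are told not to use "any other method of relieving dry eye symptoms, including any of the following", and the list that follows includes Restasis and Xiidra. Exclusion criterion 21 also bars both drugs for 60 days before enrollment and requires willingness to stay off them.
- **Worsening (11.6, item 3).** Worsening of symptoms is recognised as possible, and "if any untoward or worsening signs of ocular surface disease are observed, they will be treated appropriately". No drug is named.
- **Accounting (12.6 and 15).** Subjects are accounted for by visit with reasons for dropout, and "All protocol deviations will be documented using the Protocol Deviation form".
- **Design and analysis (7, 12.1, 12.3, 12.7).** The study is single-arm and exploratory, with no hypothesis, no pass/fail criterion and descriptive statistics only.

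**The concern.** Use of a dry eye drug during follow-up is a post-treatment event, and subjects whose eyes are not improving are the likeliest users. A rule that removes them selects partly on outcome. In a randomised study a similar selection might operate in both arms. Here the mean change from baseline is the whole effectiveness result, so nothing offsets it, and 14.2 allows publication for scientific and marketing purposes.

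Two features of the plan add to this. The exclusion in 12.5 applies to the subject, so someone who starts a drug at or after the Week 1 visit also loses Week 1 values recorded before it. And no effectiveness summary is planned on any other population, so the excluded subjects' outcomes would not be reported.

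**Working it through.** The plan gives no sample size, power or precision figure, so there is no stated number to reproduce. The check has two parts.

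**1. Can exclusion follow from response?**

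Table 2 places Week 1 at Day 5-9 and the 1-month visit at Day 21-35. Treatment begun at the Week 1 visit would run for between 21 − 9 = 12 and 35 − 5 = 30 days before the 1-month exams. There is time for a worsening subject to be treated, and so excluded, before the last measurement. Treatment begun after the 1-month exams cannot affect any recorded value. For the route to operate, the treatment given under 11.6 must be Xiidra or Restasis, or another step judged a major deviation. The documents permit this inference but do not state it.

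The eye/subject difference between 12.4 and 12.5 matters only if a drug is used in one eye. If it is used in both, the two readings exclude the same data.

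**2. How large would the shift be?**

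Inputs from the documents:
- N = 30, the maximum (9.2).
- Pilot TBUT change at 1 month: 11.7 s, SD 2.6 (5.2). Table 1 gives the pilot arm as 24 eyes of 12 subjects.

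Assumptions not in the documents:
- k = 1 to 3 subjects are excluded.
- The pilot mean and SD apply per subject.
- The response of those excluded is as set out in each scenario.

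Formula: excess of the per-protocol mean over the all-treated mean = (k/N) × (mean change of those retained − mean change of those excluded).

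| Scenario for those excluded | k = 1 | k = 2 | k = 3 |
|---|---|---|---|
| The k lowest of 30 normal responders (simulated, 200,000 replicates; all-treated mean 11.7, SD 2.6) | 0.18 s | 0.34 s | 0.48 s |
| Half response: (k/30) × (11.7 − 5.85) | 0.195 s | 0.39 s | 0.585 s |
| No change: (k/30) × (11.7 − 0) | 0.39 s | 0.78 s | 1.17 s |

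The first row is 1.6% to 4.1% of 11.7 s. The last row is 3.3% to 10%, and there the all-treated means would be 11.31, 10.92 and 10.53 s. With k = 0 every entry is zero.

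The last row is close to an extreme case: zero change lies 11.7/2.6 = 4.5 pilot SDs below the pilot mean.

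**Scale against sampling error (k = 3, no change).**
- Using retained subjects only, the standard error is 2.6/√27 = 0.50 s, and 1.17/0.50 = 2.3. This leaves the excluded subjects' spread out of the yardstick.
- The all-treated variance is [26 × 2.6² + (27 × 3/30) × 11.7²]/29 = (175.8 + 369.6)/29 = 18.8, so the SD is 4.3 s. The standard error is 4.3/√30 = 0.79 s, and 1.17/0.79 = 1.5. This is the fairer comparison.

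**Smaller true effect.** If the mean change were 5 s (assumed), the no-change row becomes 5k/30 = 0.17 to 0.50 s.

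**The case against.** The strongest objection is that the plan does not set up the route by which poor responders would be excluded. Section 11.6 names no drug, 9.5.4 forbids both named drugs, and the permitted relief, Refresh Plus, excludes nobody. Because 12.5 gives no timing, its wording also covers use inside the 60-day washout, which is an eligibility breach unrelated to response. In the pilot all 24 subjects completed 6 months, and "No adverse events were reported in either group", so the number affected may well be zero. All of this stands. It limits how likely and how large the effect is. It does not remove the rule, which can act on a post-treatment event tied to outcome.

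A second objection is that the accounting in 12.6, the deviation forms in section 15 and the safety set in 12.4 would reveal the exclusions. This stands in part. A reader might infer that exclusions would be hidden, and the documents do not support that. What is missing is narrower: no section commits to reporting how the excluded subjects fared.

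The third is that an exploratory, descriptive study has nothing riding on the choice of population. No decision rule is affected, which lowers the severity. The estimate is still the study's product.

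**Conclusion.** The point holds as a modest reporting weakness. The only effectiveness population can exclude subjects because of something that happens after treatment and is plausibly linked to poor response, and no comparison on all treated subjects is planned.

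The likely size runs from zero to about 0.6 s on an 11.7 s change. It reaches 1.17 s only if three of 30 subjects are excluded and none of them changed at all. The number excluded, their response and the use of pilot values are assumptions.

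Three stronger readings are not supported:
- **That the plan expects worsening subjects to receive Xiidra or Restasis.** It bars both and names no treatment for worsening.
- **That every method barred in 9.5.4 removes a subject.** That depends on what counts as major, and only the two drugs are specified.
- **That a shift of 1.17 s, or 2.3 standard errors, is to be expected.** That is a near-extreme scenario measured against the spread of retained subjects only.

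Safety reporting is not affected, because all attempted subjects are in the safety analysis.

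**What to change.** Keep per-protocol as the primary population and add to 12.5:

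1. The same descriptive summaries at Week 1 and 1 month for all treated subjects with follow-up data, whatever other treatment they used, shown beside the per-protocol results.
2. For Xiidra or Restasis use that starts after the TearCare procedure, exclusion from per-protocol of only the values recorded after the drug began, so that earlier Week 1 values are kept. The new text should use one unit, subject or eye, throughout.
3. The number of subjects excluded from per-protocol, with reasons.

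Item 2 repairs Week 1 only. At 1 month the subject is still absent from per-protocol, which is why item 1 is needed.

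The cost is a few sentences and one descriptive table. Table 2 already collects medication use and the endpoints at both follow-up visits, and deviations are already documented, so no new visit is required. The downside is that the all-treated mean may be slightly less favourable and will include the effect of other treatment in a few subjects. For that second reason it may understate the gaps in the table above, and it should sit beside the per-protocol result and not replace it. If nobody is excluded, the two summaries agree.

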12.6 SUBJECT ACCOUNTABILITY

A complete accounting of subjects by visit will be provided, including reasons for dropout, if known.

12.7 STATISTICAL DESIGN, METHOD & ANALYTICAL PROCEDURES TO BE USED

Only basic descriptive statistics will be used to analyze data from the study.

12.8 INTERIM ANALYSIS AND EARLY TERMINATION CRITERIA

No interim analysis or early termination criteria are planned for this study.

12.9 DEVIATION FROM THE STATISTICAL PLAN

Any deviations from the statistical plan will be noted in the final report.

13 MONITORING PROCEDURES

Sight Sciences or contract research organization (CRO) personnel will monitor the study in a manner consistent with FDA regulations, good clinical practices and the clinical research standards adopted by Sight Sciences. Study monitoring will involve the following elements:

- Site Qualification: For sites that have not already been qualified for another Sight Sciences study, Sight Sciences or CRO personnel will meet with investigators and clinical study staff prior to the initiation of the study in order to review the adequacy of the subject population, facilities, and equipment with respect to the needs of the study, and to familiarize the investigator with the study protocol.

- Site Initiation: Sight Sciences or CRO personnel will meet with the investigator(s) and clinical study staff when the site is ready to begin enrolling subjects in order to train them in how to properly select subjects, perform the study procedure, and record study data. This visit will include, but not be limited to a review of the following:
 - Detailed review of the protocol
 - Informed consent procedures
 - Instruction in how to use the TearCare System
 - Records and reports
- Interim Monitoring: Due to the small sample size and one month study duration, interim monitoring may not be required. Sight Sciences or CRO personnel may visit the clinical site during the study to review charts and to perform source document verification, to ensure proper adherence to the study protocol, and to review regulatory documents.
- Study Closure: At the conclusion of the trial there will be a study closure visit during which several actions, including but not limited to the following, will be performed:
 - A final inspection of the study binder
 - Accountability and return of all devices and study materials to the sponsor
 - Discussion of record retention requirements with the investigator
 - Close-out notification to the IRB

14 DATA AND QUALITY MANAGEMENT

All study-related data will be recorded on Case Report Forms. When subjects are enrolled in the study, they will receive a unique study identifier, which will be used to identify them on all Case Report Forms. The Enrollment log containing the subject identifying information and the subject study id will be maintained under the investigator's control at all times. No subject-identifying information will leave the site.

14.1 DATABASE MANAGEMENT

Data Management will be performed by Sight Sciences who will create a database or spreadsheet in which the study data will be entered.

14.2 CONFIDENTIALITY

All medical records associated with the clinical investigation will be made available for review by Sight Sciences personnel, its contract research organization (CRO) and

governmental/regulatory agencies involved. The results of the study may be published in the future for scientific and marketing purposes, but the identity (name) of each subject will not be revealed. All records will be stored in a secure area at the investigator's facility, the CRO, the data management firm and at Sight Sciences, Inc.

14.3 SOURCE DATA AND CASE REPORT FORMS

Data will be collected directly on the study worksheets provided by the sponsor and these study worksheets will serve as the source data.

Source data and study worksheets are to be maintained at the site in the subject records or in the medical records. All entries must be made in black or blue ink and changes must be made by strike-through only with date and initials or signature. All source documents must be completed and signed by the authorized study personnel (e.g., study coordinator). No "white-out" is to be used on the source documents.

14.4 RETENTION PERIOD

Clinical sites are to retain any and all clinical trial material (documentation, photographs, etc.) for a period of two years from the date the marketing application is approved or two years after the investigation has been discontinued, or as directed by their institutional document retention requirements, whichever is the longest. After that time, the items must be returned to Sight Sciences for archiving. Unused medical devices are to be returned to the sponsor at the conclusion of the enrollment period.

15 PROTOCOL MODIFICATIONS AND DEVIATIONS

Protocol modifications may occur during the study. Each will be approved by the sponsor before implementation. Each will undergo Institutional Review Board (IRB) review and approval, as necessary.

Any deviations from this protocol intended to protect the life or physical well-being of a subject in an emergency are to be reported to Sight Sciences, Inc. as well as the IRB as soon as possible, and no later than 5 working days after the emergency occurred.

All protocol deviations will be documented using the Protocol Deviation form.

16 DEVICE FAILURES AND MALFUNCTIONS

All device failures or malfunctions should be recorded on the Device Deficiency Form and reported to Sight Sciences Customer Service [REDACTED]

If the TearCare procedure cannot be completed due to a product failure or malfunction, the procedure may be rescheduled for a different day. Every effort should be made to reschedule the procedure within the next 7 calendar days of the Baseline visit.

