Exclusion Criteria (continued)	
ocular or corneal sensation
 
17. Corneal surface abnormalities such as corneal epithelial defects (other than punctate staining), ulcers, corneal epithelial dystrophies, keratoconus, and ectatic disease of the cornea
 
18. Punctal occlusion or punctal plug placement within 30 days prior to enrollment
 
19. Systemic diseases resulting in dry eye (e.g. autoimmune diseases such as Sjogren's syndrome, rheumatoid arthritis, lupus, Graves' disease, sarcoidosis, etc.)
 
20. Allergies to silicone tissue adhesives
 
21. Use of Restasis or Xiidra within 60 days prior to enrollment. Subject must also be willing to remain off these drugs for the duration of the study.
 
22. Use of antihistamines (oral or topical) within 10 days prior to enrollment. Subject must also be willing remain off antihistamines for the duration of the study.
 
23. Subject is currently on a systemic medication(s) (other than anti-histamines) that is known to cause ocular dryness (e.g. diuretics, anti-hypertensives, anti-depressants, hormone therapy) and whose dose of this medication(s) has not been stable within 30 days prior to enrollment. There must be no anticipated adjustments to the dose of these medications for the duration of the trial.
 
24. Subject has taken or is currently taking Accutane
 
25. Subject requires chronic use (i.e. for any portion of the study) of topical ophthalmic antibiotics, anti-glaucoma medications, steroids, non-steroidal anti-inflammatory medications or who has been on any of these medications within 30 days prior to enrollment
 
26. Subject is currently using Retin A or Latisse
 
27. Participation in another ophthalmic clinical trial within one year prior to enrollment. Subject must also be willing to refrain from another ophthalmic study for the duration of the study.
 
28. Co-existing condition, either ocular or non-ocular that, in the judgement of the investigator could affect the safety or effectiveness of treatment or the compliance of the subject to the protocol. Subjects who are pregnant or nursing or have active, wet macular degeneration are excluded.

Number of Subjects	Up to 30

Study of the TearCare® System in Dry Eye Disease
Protocol 06001 Rev C

Number of Sites	2-3
Study Duration for Each Subject	1 month
Schedule of Visits	Baseline, Week 1, 1 Month
Treatments	TearCare procedure at Baseline

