6.2 SAFETY ENDPOINTS

Safety will be assessed by evaluating the following measures over time:

- Device-related adverse events (all adverse events will be recorded)
- Best spectacle-corrected visual acuity (Snellen)

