7 STUDY DESIGN

This is a prospective, single-arm, exploratory treatment study. This is a post-market study intended to collect clinical data regarding the safety and effectiveness of the TearCare System. To reduce potential bias in the study, study staff performing the endpoint assessments will be independent of the clinician performing the TearCare procedure.

In this study, all subjects will receive the TearCare procedure. The TearCare procedure includes an in-office 15 minute treatment session with the TearCare System immediately (i.e. within 3 minutes) followed by manual expression of the meibomian glands using the Express Forceps. Subjects will receive one in-office TearCare procedure at the baseline visit and will then have follow-up visits at 1 week and 1 month.

This study will be conducted at 2-3 sites in the United States.

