9 STUDY PROCEDURES

9.1 STUDY SCHEDULE

The Study Schedule is shown below in Table 2.

Table 2: Study Visit Schedule

Visit (Visit Window)	Baseline (Day 0)	Wk 1 (Day 5-9)	1 Mo (Day 21 – 35)
Informed Consent	X		
Demographics, Ocular & Medical History	X		
Medication use	X	X	X
OSDI*	X	X	X
Best Spectacle corrected visual acuity (Snellen)*	X	X	X
Slit Lamp Exam*	X	X	X
Tear Breakup Time*	X	X	X
Corneal Staining*	X	X	X
Conjunctival Staining*	X	X	X
Meibomian Gland Secretion Scoring*	X	X	X
TearCare Treatment	X		
AE Assessment*	X	X	X
Lubricant Drops Log			X

* Endpoint assessment should be performed by an independent study staff who does not perform the TearCare procedure on study subjects.

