9.2 NUMBER OF SUBJECTS AND DURATION OF FOLLOW-UP

Up to 30 subjects will be enrolled and treated in the study. All subjects will be followed for 1 month.

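### Does rescheduling a failed procedure by up to 7 days leave the Week 1 visit at the wrong time after treatment?

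*Combined protocol and SAP*

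**What the plan says.** The combined protocol and SAP normally makes the baseline day and the treatment day the same day. The synopsis (Section 1) lists "TearCare procedure at Baseline". Section 7 says: "Subjects will receive one in-office TearCare procedure at the baseline visit and will then have follow-up visits at 1 week and 1 month". Table 2 in Section 9.1 places the treatment in the Baseline column, labelled Day 0, and sets windows of Days 5-9 for Week 1 and Days 21-35 for 1 Month. Section 9.6 sends sites back to Table 2 for follow-up, and Section 9.2 states: "All subjects will be followed for 1 month".

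Section 16 covers the exception. If a product failure or malfunction prevents completion, "the procedure may be rescheduled for a different day", and then: "Every effort should be made to reschedule the procedure within the next 7 calendar days of the Baseline visit". The 7 days are a best-effort target, not a limit. No section says whether the follow-up windows then run from the Baseline visit or from the rescheduled procedure.

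On analysis, Section 12.7 says: "Only basic descriptive statistics will be used to analyze data from the study". Section 12.3 sets no pass/fail criterion, and Section 6.1 names no time point for the primary endpoint.

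**The concern.** Once Section 16 separates the two dates, a site that counts Table 2 from the Baseline visit could hold a Week 1 visit too soon after treatment, or even before it. The value would still be entered as Week 1. That would affect tear break-up time and the other effectiveness scores. It would also affect safety: Section 6.2 states "Safety will be assessed by evaluating the following measures over time", and Table 2 schedules visual acuity, slit lamp examination and adverse-event assessment at Week 1.

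Nothing in the analysis plan would remove such a value. The per-protocol rule in Section 12.5 asks for only one visit after treatment, and the 1 Month visit can supply it. With at most 30 subjects, a few mistimed values could shift a Week 1 mean.

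**Working it through.** **Inputs.** Week 1 window Days 5-9 and 1 Month window Days 21-35 (Table 2); treatment planned for Day 0 (Table 2, Section 7); rescheduled treatment on Day d, with d from 1 to 7 if the Section 16 target is met.

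**Formulas, counting the windows literally from the Baseline visit.**
- Days since treatment at an in-window visit: 5 − d to 9 − d (Week 1) and 21 − d to 35 − d (1 Month).
- Week 1 window days that fall 5-9 days after treatment: max(0, 5 − d), of 5.
- 1 Month window days that fall 21-35 days after treatment: 15 − d, of 15.

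The row d = 0 reproduces the plan's own windows.

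| d | Week 1: days since treatment | On target (of 5) | Before treatment (of 5) | 1 Month: days since treatment | On target (of 15) |
|---|---|---|---|---|---|
| 0 | 5 to 9 | 5 | 0 | 21 to 35 | 15 |
| 1 | 4 to 8 | 4 | 0 | 20 to 34 | 14 |
| 2 | 3 to 7 | 3 | 0 | 19 to 33 | 13 |
| 3 | 2 to 6 | 2 | 0 | 18 to 32 | 12 |
| 4 | 1 to 5 | 1 | 0 | 17 to 31 | 11 |
| 5 | 0 to 4 | 0 | 0 | 16 to 30 | 10 |
| 6 | −1 to 3 | 0 | 1 | 15 to 29 | 9 |
| 7 | −2 to 2 | 0 | 2 | 14 to 28 | 8 |

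So the literal count fails outright only for d = 5, 6 or 7, and only at Week 1. For d = 1 to 4, some Week 1 days satisfy both counts. At 1 Month, Days 21 + d to 35 satisfy both counts for every d up to 7; at d = 7 these are Days 28-35.

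**Which count the text supports.** Table 2 puts the treatment itself in the Day 0 column, so Day 0 is the treatment day as much as the baseline day. Section 7 places the procedure first and the follow-up visits after it. Section 9.6 requires the follow-up examiner to be someone other than the clinician who did the procedure, which presupposes that it has been done. Section 12.5 defines the analysis population by a visit after treatment. A Week 1 follow-up held before the procedure would conflict with all four.

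**Windows counted from treatment.** Week 1 is Days 5 + d to 9 + d, and 1 Month is Days 21 + d to 35 + d. At d = 7 these are Days 12-16 and 28-42. Every visit is then at its intended time.

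**Size.** If k of n subjects had a Week 1 value with no treatment effect and the rest had mean change m, the Week 1 mean would be m(n − k)/n, a relative loss of k/n. For one subject at the maximum n = 30 this is 1/30 = 3.3%. The k is an assumption, since no device-failure rate is given. Nor is zero effect established: within the target, a visit before the redo is possible only at d = 6 (1 of 5 days) or d = 7 (2 of 5 days), and the documents say nothing about tear break-up time 0 to 4 days after treatment. Turning the percentage into seconds would mean borrowing the pilot's 4-week change of 11.7 s (Section 5.2), which came from 12 minutes of heating where this study uses 15. That would not measure this gap.

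**The case for a change.** The strongest case for a change is that the protocol foresaw device failure, wrote a rule for it and left the rule unfinished. Relying on intent does not fully settle the matter. For d = 5 to 7, a visit 5-9 days after treatment falls on Days 10-16 and so outside the printed Days 5-9. A site that follows the intent may have to log a deviation under Section 15. Section 12.5 excludes subjects with major deviations, and beyond its mention of dry-eye medications it does not define the term. Two or three sites could choose differently, and a clarifying sentence would be cheap.

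What stands is that the anchor is unstated and that sites could differ. The rest carries less weight. It would be hard to call a visit a major deviation when it is held at its intended time after a procedure that Section 16 permits. The 1 Month visit can meet both counts throughout the target week.

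Nor is counting everything from completion a clear gain. Section 16 concerns procedures that could not be completed, so a subject may already have had some exposure on Day 0, and Section 12.4 counts every attempted subject for safety. Moving the whole schedule would shift the first planned safety check after a failed attempt from Days 5-9 to as late as Days 12-16 at d = 7.

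**Conclusion.** The documents do leave the anchor date unstated after a rescheduled procedure, and the day counts above are exact. This is a missing detail for a contingency, and no change to the plan is needed. Reaching a misleading Week 1 value takes a device failure, rescheduling to Day 5 or later, and a literal count from the Baseline visit that Table 2 and Section 7 point against.

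Timing can be checked afterwards. Section 18.3.3 requires records of each subject's exposure to the device, Section 16 requires failures to be recorded on a form, and Section 15 does the same for deviations. An analyst should therefore be able to derive days since treatment and set aside or annotate an odd value, and Section 12.9 provides for noting departures from the statistical plan in the final report.

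Within the 7-day target, at least 8 of 15 days of the 1 Month window stay on target. No conclusion of the study turns on Week 1 alone: it has no designated primary role and no criterion attached to it. This conclusion assumes that device failures are few, which the documents neither state nor contradict, and that the 7-day target is generally met. Later treatment would widen the mismatch under a literal count: at d = 9 the whole Week 1 window falls on or before the treatment day.
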